18. LIST OF TABLES

Not applicable.

19. LIST OF FIGURES

Not applicable.

20. ANNEX 1. LIST OF STAND-ALONE DOCUMENTS

Number	Document reference number	Date	Title
	v1.0	12-Feb-20	English-USA-Qolissy Shortform (Children)-v1.0-12-Feb-20 English-USA-Qolissy Shortform (Parents)-v1.0-12-Feb-20
	Original	1990	CHAQ Version 1990 Original version Singh G et al.

21. ANNEX 2. ADDITIONAL INFORMATION

Not applicable.

13.1. Planned Table Descriptions.....	18
13.2. Planned Listing Descriptions.....	21
13.3. Planned Figure Descriptions	23
14. Tables, Listings, and Listing Shells	24
14.1. Standard Layout for all Tables, Listings, and Figures	24
Appendix 1: Premier Research Library of Abbreviations	25
Appendix 2: Calculation of the Height-for-Age SDS	26

List of Tables

Table 1: Anthropometric Measurements.....	6
Table 2: Schedule of Events.....	11
Table 3: Demographic Data Summary Tables and Figures	19
Table 4: Anthropometric Data.....	20
Table 5: Safety Data.....	21
Table 6: Planned Listings.....	22
Table 7: Planned Figures.....	23

1. Overview

This master statistical analysis plan (SAP) describes the planned analysis and reporting for Pfizer protocol number C4181001 (An International, Prospective Registry Investigating the Natural History of Children with Achondroplasia), dated 31-Jan-2019, version 2.0.

This study uses a primary master SAP and may require supplemental SAPs as well. An advantage of this study design is its ability to answer questions that emerge during the course of the study¹. Subsequent and supplemental SAPs - triggered by new research questions emerging after the initial master SAP - can be developed when enough data become available, including data from other studies, to analyze a particular research question not included in this master SAP.

Reference materials for this statistical plan include the protocol, the anthropometric manual, and the accompanying sample data collection documents. Operational aspects related to collection and timing of planned clinical assessments are not repeated in this SAP unless relevant to the planned analysis.

The structure and content of this SAP provide sufficient detail to meet the requirements identified by the Food and Drug Administration, European Medicines Agency, and International Conference on Harmonization of Technical Requirements for Registration of Pharmaceuticals for Human Use: Guidance on Statistical Principles in Clinical Trials². All work planned and reported for this SAP will follow internationally accepted guidelines, published by the American Statistical Association³ and the Royal Statistical Society⁴, for statistical practice.

The planned analyses identified in this SAP may be included in clinical study reports (CSRs), regulatory submissions, or future manuscripts. CCI

The statistical plan described hereafter is an *a priori* plan. It will be submitted to file prior to any inferential or descriptive analysis of data pertaining to Pfizer's study C4181001.

2. Study Objectives and Endpoints

2.1. Study Objectives

To investigate the natural history of children with achondroplasia in terms of:

- anthropometric characteristics
- achondroplasia-related symptoms, tests, and treatments
- biomarkers of bone growth

2.2. Study Endpoints

2.2.1. Safety Endpoints

Not applicable.

2.2.2. Efficacy Endpoints

Not applicable.

2.2.3. Anthropometric Endpoints

2.2.3.1. Anthropometric Measurements

Anthropometric measurements will be done at all study visits and measurement results will be reported in the electronic case report form (eCRF). Anthropometric measurements will be performed according to the study-specific Anthropometric Measurement Manual.

The anthropometric endpoints of the study include specific measurements assessed at every visit or yearly. Moreover, the anthropometric manual requires performing 3 valid measurements for all endpoints during a visit, with the exception of body weight.

Table 1: Anthropometric Measurements

Measurements	Unit	Age group	Visit	# of valid measurements
Standing height	cm	≥2 years	Every visit	3
Height in supine position	cm	<2 years	Every visit	3
Sitting height	cm	≥2 years	Every visit	3
Crown-rump length	cm	<2 years	Every visit	3
Knee height	cm	All	Every visit	3
Head Circumference	cm	All	Every visit	3
Arm Span	cm	All	Every visit	3
Elbow extension angle	degrees	All	Every visit	3
Knee extension angle	degrees	All	Every visit	3
Body weight	kg	All	Every visit	1
Forehead Results	cm	All	Every visit	3
Top of nose results	cm	All	Every visit	3
Base of nose results	cm	All	Every visit	3
Waist circumference	cm	All	Yearly	3
Chest circumference	cm	All	Yearly	3

2.2.3.2. Derived Anthropometric Endpoints

Five additional anthropometric endpoints will be derived:

1. Height Growth (HG)

$$HG_i = \frac{OH_i - OH_0}{RH_i - RH_0}$$

where:

OH_i = Observed Height in cm at visit i

OH_0 = Observed Height in cm at baseline

RH_i = Achondroplasia Reference Height at i (Merker et al., 2018)⁹

RH_0 = Achondroplasia Reference Height at baseline

HG will be calculated every 3 months after baseline.

2. Sitting height/standing height (%)

The ratio (%) between the sitting height and the standing height will be calculated for all subjects.

3. Arm span/standing height (%)

The ratio (%) between the arm span and the standing height will be calculated for all subjects.

4. Difference between arm span and standing height (cm)

The difference between the arm span and the standing height will be calculated as:
arm span (cm) – standing height (cm)

5. Height Standard Deviation Score (SDS)

The SDS for a given height or length in cm will be calculated using the LMS method

$$SDS = \frac{\left(\frac{\text{height in cm}}{M}\right)^L - 1}{LS}, \quad L \neq 0$$

$$SDS = \frac{1}{S} \ln\left(\frac{\text{height in cm}}{M}\right), \quad L = 0$$

where L, M, and S are the interpolated values between the neighbouring values from the standard tables corresponding to the gender and to the exact age of the child. If the month is missing in the date of birth then the SDS will be set to missing.

L, M, and S, provided in the standard tables, are the tabulated fitted values of Box-Cox power, median, and coefficient of variation corresponding to the standard population, respectively.

If $L=1$ the formula for calculating the SDS can be written as:

$$SDS = \frac{\text{observed value} - \text{median value of the reference population}}{\text{standard deviation value of the reference population}}$$

where the median value is M and the standard deviation is $M \times S$.

The same method will be applied for both the standing height and the recumbent length.

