	
Exclusion criteria:
 
The following criteria exclude participation:
 
 1. The participant has a diagnosis of hypochondroplasia or any short stature condition other than achondroplasia (eg, spondyloepiphyseal dysplasia congenital [SEDC], pseudo achondroplasia, trisomy 21). 2. The participant has any medical condition that may impact growth or where the treatment is known to impact growth, such as but not limited to hypothyroidism or hyperthyroidism, insulin-requiring diabetes mellitus, autoimmune inflammatory disease (including celiac disease, systemic lupus erthematosus (SLE), juvenile dermatomyositis, scleroderma, and others), autonomic neuropathy, or inflammatory bowel disease. 3. Treatment in the previous 12 months prior to consent/assent with growth hormone, insulin-like growth factor 1 (IGF-1), anabolic steroids, or any other drug expected to affect growth velocity. 4. Any surgery that affects the growth plate of the long bones that is planned, or has occurred in the past 18 months. 5. Participation in any interventional study (investigational product or device) for treatment of achondroplasia or short stature. 6. Has had bone-related surgery impacting assessment of anthropometric measurements or is expected to have it during the study period. Participants with previous limb-lengthening surgery may enroll if surgery occurred at least 18 months prior to the date of consent/assent and healing is complete without sequelae as determined by the investigator. 7. Has any condition or circumstance that in the view of the investigator places the child at high risk of poor compliance with the visit schedule or of not completing the study. 8. Any concurrent disease or condition that in the view of the investigator would interfere with study participation.

PLANNED STUDY SITES
	
There will be a total of approximately 35 study sites globally.

CRITERIA FOR EVALUATION
	
Anthropometric measurements will be the primary assessments, including but not limited to Annual Growth Velocity (AGV). Clinical course of children with achondroplasia with focus on achondroplasia-related symptoms, tests and treatments.

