5. SCHEDULE OF ACTIVITIES

STUDY PROCEDURES and **ASSESSMENTS** sections of the protocol for detailed information on each procedure and assessment required for compliance with the protocol.

The investigator may schedule visits (unplanned visits) in addition to those listed in the schedule of activities table, in order to conduct evaluations or assessments required to protect the well-being of the participant.

Procedure/Assessment	Screening Visit ^a	Baseline Visit ^b	Every 3 Months ^c (±3 weeks)	End of Study Visit ^d (±3 weeks)
Informed Consent & Assent (as applicable)	X			
Eligibility criteria	X	X		
Demographics	X			
Specific Medical & Surgical History	X	X		
Physical Examination		X	X	X
Genetic Confirmation of Achondroplasia ^e		X		
Anthropometric Measurements		X	X	X
Achondroplasia-related complications, tests & treatments		X	X	X
Non-achondroplasia-related important medical conditions and treatments ^f		X ^f	X ^f	X
Tanner Stage of Puberty ^g		X ^g	X ^g	X
Collection of Biomarker Blood Sample ^h		X	(X) Every 12 Months	
Concomitant treatments	X		X	→
Adverse event monitoring	X	X	→	→
QoLISSY Brief tool (HRQoL)		X	X	X
Childhood Health Assessment Questionnaire (CHAQ)		X	X	X
Physical activity via accelerometry (digital wearable sensors) ⁱ (selected sites only)	X	X	X	X
Gait walking assessment ^j (selected sites only)	X	X	X	X
Wearability Questionnaire of digital sensors ^k (selected sites only)	X	X	X	X

Abbreviations: → = ongoing/continuous event.

- a. Screening may be scheduled within 1 month prior to the Baseline visit.
- b. Screening visit and Baseline visit can be combined, if applicable.
- c. Three-month follow-up visits are scheduled relative to the date the Baseline Visit was conducted.
- d. The End of study visit is conducted if any one of the termination criteria listed are met or after a decision is made by the investigator to withdraw the participant from the study. The end of study visit may be combined with a three-monthly visit.
- e. If not available in medical records, then the result of genetic testing should become available as soon as possible, but not later than prior to end of study visit.
- f. Any important non-achondroplasia related important medical condition (s) that may potentially jeopardize the participant's health and any treatment based on the medical judgment of the investigator that may affect the participant's growth trajectory (see [Section 11.3](#)).

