The design of future interventional trials with potentially disease-modifying therapies to treat the underlying morphological disproportions of the skull and skeletal system will benefit from a better understanding of the natural history of the disease course in the youngest group of participants, where final skeletal and morphological proportions are being established prior to entering the final longitudinal growth phase during later stages of childhood and adolescents.

The rationale for the prospective, longitudinal registry design to collect information about important achondroplasia-related symptoms, tests and treatments is the aim to characterize the natural history of the disease course in the youngest participants in relation to symptoms and development of complications, the level of actual disease burden over time due to tests and treatments, as well as data to support identification of possible risk factors.

Despite its importance as a key parameter, growth velocity is difficult to determine in real time in achondroplasia, because skeletal growth is slow and clinical tools to accurately detect very small increments of growth do not exist. During development, bone is created by a process called endochondral ossification, which results in the production of a fragment of type X collagen. Endochondral ossification also occurs during long bone growth and fracture healing.

Recently, Coghlan et al. discovered that the type X collagen fragment could be isolated from blood and its concentration correlated with skeletal growth velocity (Coghlan 2017).⁸

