7. RESEARCH QUESTION AND OBJECTIVES

Primary Objective(s):	Primary Endpoint(s):

 Collection of longitudinal anthropometric and disease-related complication data in children with achondroplasia. 	Standing height, sitting height, knee height, head circumference, arm span, length of the legs (calculated as the difference between standing and sitting height) and achondroplasia related AEs.
Secondary Objective(s):	Secondary Endpoint(s):

 Investigation of potential serum biomarkers in children with achondroplasia. 	
 Baseline and post-baseline measurements of serum collagen X marker.
CCI [REDACTED]	[REDACTED]
[REDACTED]	[REDACTED]
[REDACTED]	[REDACTED]

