7.2. Anthropometric Parameters

Anthropometric data will be collected in a prospective and standardized fashion to allow correlation to disease severity and serve as baseline data for future interventional clinical trials. Standing height is most commonly used measure of growth in participants. As one of the morphological characteristics of participant with achondroplasia is the shorter limbs, any biomarker used for the study of these participants should be able to reflect this impaired growth.

The arm span and the length of the legs (calculated as the difference between standing and sitting height) will be used as robust measures of the growth of the limbs. All other measurements collected are considered **CCI** in nature and may be used to support further endpoints in later development trials.

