11.5. Data Analysis

Detailed methodology for summary and statistical analyses of data collected in this study will be documented in a statistical analysis plan (SAP), which will be dated, filed and maintained by the sponsor. The SAP may modify the plans outlined in the protocol; any major modifications of primary endpoint definitions or their analyses would be reflected in a protocol amendment.

As the main purpose of this study is to collect data to be used as reference for future interventional clinical studies, no hypothesis testing will be made.

A detailed master statistical analysis plan (SAP) will be developed covering the analytical principles and statistical techniques to be employed both for interim and final analysis. This study plans a primary master SAP, as well as supplemental SAPs. An advantage of this study design is its ability to answer questions that emerge during the study.

Subsequent and supplemental SAPs - triggered by new research questions emerging after the initial master SAP is developed or needed because the registry may evolve - can be developed when enough data become available to analyze a particular research question not included in the master SAP.

The main purpose of this study is descriptive.

Generally, descriptive statistics will be reported for all measured variables captured in this study. Derived Anthropometric measurements include:

- Annual Growth Velocity (AGV);
- Height Standard Deviation Score (SDS) with reference to normal population;
- Height SDS with reference to achondroplasia population;
- Sitting height/standing height (%) (or length: crown-rump length);
- Difference or ratio of Arm span/standing height/length (%);
- Knee height: lower segment length (lower segment=standing height – sitting height);
- Ratios between the cranial measurements taken.

Continuous (quantitative) variable summaries will include the number of participants (n) with non-missing values, number of missing values, mean and 95% confidence interval, standard deviation, median, minimum, and maximum.

Continuous variables may be classed into groups and analyzed as a categorical variable when appropriate. Categorical (qualitative) variable summaries will include the frequency and percentage of participants who are in the particular category or each possible value.

Event data will generally be listed. In case of frequent events tabulations might be considered.

Interim analyses will be performed on a regular basis.

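### The SAP gives no leg length in cm, a protocol primary endpoint, and leaves Annual Growth Velocity without a formula, table or figure

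*SAP*

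**What the plan says.** **Protocol v3.0.** The primary endpoint row in Section 7 names six anthropometric measures. The sixth is the "length of the legs (calculated as the difference between standing and sitting height". Section 7.2 says of arm span and leg length together that they "will be used as robust measures of the growth of the limbs". In the Section 3 Summary, the criteria for evaluation read "Anthropometric measurements will be the primary assessments, including but not limited to Annual Growth Velocity (AGV". Section 6 says "Despite its importance as a key parameter, growth velocity is difficult to determine in real time in achondroplasia". The derived measurements in Section 11.5 start with "Annual Growth Velocity (AGV" and also include "Knee height: lower segment length" and ratios between the cranial measurements.

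**SAP.** Section 1 says the plan was written to protocol v2.0 of 31-Jan-2019. Section 2.2.3.2 opens with "Five additional anthropometric endpoints will be derived" and names Height Growth (HG), sitting/standing height (%), arm span/standing height (%), arm span minus standing height (cm) and height SDS. Section 6.1.5 repeats these and adds change from baseline. AGV occurs only in the Appendix 1 abbreviations and as the title of Listing 16.2.6.5. The tables and figure for HG cite that listing as their support. Section 10 records no change from the planned analysis.

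**The concern.** Section 11.5 of the protocol gives the registry's main purpose as reference data for later interventional studies. Designers of such studies will look for limb length in cm and for yearly growth in cm/year, each with a mean and a spread by sex and age. If the SAP is followed as written, one primary endpoint has no summary of its own, and growth rate is replaced by a ratio in other units.

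An undefined AGV also leaves a choice open until data are in hand. Over 60 months of 3-monthly visits it could mean 5 consecutive annual values per child, or (60 − 12)/3 + 1 = 17 overlapping 12-month values. These give different summaries. The SAP describes itself as fixed before any analysis, so the choice belongs in it.

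**Working it through.** No sample size or test is involved, so there is no plan figure to reproduce. The check sets the lists side by side and then asks whether a planned output could stand in for each missing one.

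**1. Section 7 against SAP Table 4.**

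| Section 7 primary measure | SAP table |
|---|---|
| Standing height | 14.2.1.1 |
| Sitting height | 14.2.1.3 |
| Knee height | 14.2.1.5 |
| Head circumference | 14.2.1.6 |
| Arm span | 14.2.1.7 |
| Leg length | none |

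One of six has no table. The SAP does derive another difference in cm (arm span minus standing height), so differences are not excluded on principle.

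**2. Section 11.5 against SAP 2.2.3.2 and 6.1.5.** Of seven derived measures, the two height SDSs, the sitting/standing ratio and the arm span measure are present. AGV, knee height to lower segment and the cranial ratios are absent: 3 of 7. Section 11.5 defines lower segment as standing minus sitting height, so leg length is also the denominator of one of these.

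**3. Can leg length be read from other tables?** In part.
- Mean leg length = mean standing − mean sitting height, if the same children are in both tables.
- The ratio R gives relative leg length, 100% − R, with its spread.
- Adding the SD of R to the two height SDs gives a first-order SD in cm. With assumed standing height 98.5 cm (SD 4.0) and an independent ratio of 66% (SD 2%), the SD is √[(0.34 × 4.0)² + (98.5 × 0.02)²] = √(1.85 + 3.88) = 2.39 cm. Back-calculation from the three SDs also gives 2.39 cm.
- Table 4 lists the ratio by age group, but lists standing and sitting height without age groups. As listed, the approximation cannot be made by age group from 2 years up.

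**4. Can HG stand in for AGV?** No. HG = (height at visit − baseline height)/(reference height at visit − reference height at baseline). From the SAP Appendix 2 medians, HG = 1 corresponds to:
- boys 7 to 8 y: (99.6 − 95.8)/1 = 3.8 cm/y
- boys 1.5 to 2 y: (72.9 − 69.8)/0.5 = 6.2 cm/y
- girls 2.5 to 3 y: (76.8 − 74.3)/0.5 = 5.0 cm/y

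A child growing 4.0 cm/y therefore has HG of 1.05, 0.65 or 0.80. HG is also cumulative from baseline.

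**5. Can change from baseline stand in?** For year 1, yes. The month-12 change, tabulated with SD, median and range under SAP Section 8, approximates cm/year. From month 24 it is a cumulative gain. Subtracting tabulated means gives mean year-2 growth if the same children contribute. The variance of year-2 growth is Var(C24) + Var(C12) − 2Cov(C12, C24), where C is change from baseline, and no table gives the covariance.

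**6. Timing.** "Three-month follow-up visits are scheduled relative to the date the Baseline Visit was conducted", with ±3 weeks, and SAP 6.1.3 keeps visits as labelled.
- Year 1: 365.25 ± 21 = 344 to 386 days. The limit is 21/365.25 = 5.7%, or 0.22 cm at 3.8 cm/y.
- Later years: 365.25 ± 42 = 323 to 407 days. The limit is 42/365.25 = 11.5%, or 0.44 cm.

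These are window limits, not typical errors. If windows are used evenly (assumed), the timing SD is 21/√3 = 12.1 days in year 1 and √2 × 12.1 = 17.1 days later, or 0.13 and 0.18 cm. Against an assumed growth SD of 1.0 cm, that widens the SD by about 0.8% and 1.6%, without bias in the mean.

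**7. The supine-to-standing switch at 2 years.** If the 40% of 300 enrolled at 0-5 y are evenly spread by age (assumed), 300 × 0.40 × 2/5 = 48 enrol under 2 y. The 24 aged 0-1 y have two annual intervals starting before age 2, and the 24 aged 1-2 y have one: 48 + 24 = 72. Each child has one interval that spans the switch, so 48/72 = 67% of these intervals do.

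**The case against.** The strongest reply is that nothing is irrecoverable. Leg length is a subtraction of two collected values, SAP 6.1.6 puts all collected data in listings, Listing 16.2.6.1 holds the measurements, and SAP 4.2 lets the sponsor request further analyses. The study is descriptive and tests no hypothesis. All of this stands. It makes the gap one of planned output, not of data.

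Protocol 11.5 also lets the SAP modify the plan. But it reserves major modifications of primary endpoint definitions or their analyses for a protocol amendment, and v3.0 retains leg length. Supplemental SAPs are meant for new research questions, which an existing primary endpoint is not.

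Four stronger readings are tempting, and the documents do not support them.
- *AGV is an omitted primary endpoint.* The Summary names it among the primary assessments, but the primary row in Section 7 does not list it. Later rows of that table are blacked out.
- *SAP Section 10 is untrue.* It speaks to v2.0, whose text is not available. It does not hold against v3.0, but the documents do not show whether the version lag caused the gap.
- *The height tables will lack age groups.* Only the population column in Table 4 suggests this. SAP Section 8 calls for age-group analysis, and the table shells are a separate document. The SAP's own 2-10 year group is wide enough that adding it would still mix very different heights.
- *Visit windows make yearly change unreliable.* Step 6 shows a small effect under even use of the windows.

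**Conclusion.** The point holds and should be fixed before analysis, though it does not threaten the validity of the data. Against protocol v3.0, 1 of 6 anthropometric primary endpoints has no direct summary in cm, and 3 of the 7 derived measures in 11.5 are missing. AGV has no formula, table or figure, so no annual growth rate with its spread is planned after year 1. It would go too far to say that these quantities cannot be obtained. Mean leg length can be approximated from planned tables, year-1 growth is covered by change from baseline, and the rest can be rebuilt from listings.

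These conclusions follow from comparing the two documents and rest on no assumed figure. Assumptions enter only in the leg-length SD illustration, the typical timing error, and the 48 of 72 count.

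**What to change.** 1. Re-base the SAP on protocol v3.0.
2. Add leg length in cm to SAP 2.2.3.2, 6.1.5 and the table list: standing minus sitting height, or supine length minus crown-rump length under 2 years. Tabulate observed value and change from baseline by visit, sex and age group, keeping under and over 2 years separate.
3. Define AGV (cm/year) = (height gain between consecutive annual visits ÷ exact days between them) × 365.25. Tabulate it by study year, sex and age group. Flag intervals spanning the supine-to-standing switch and report them separately. Dropping them would remove about two thirds of the intervals starting before age 2, and the protocol's rationale stresses the youngest children. Keep HG alongside.
4. Add knee height to lower segment and the cranial ratios, or record their omission in SAP Section 10.
5. Align the population column of Tables 14.2.1.1 and 14.2.1.3 with SAP Section 8. Retitle or split Listing 16.2.6.5. Reconcile the status of AGV between the protocol Summary and Section 7.

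The cost is one SAP amendment and a few table shells, plus a protocol clarification if AGV's status changes there. No new data, visits or procedures are needed.
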